8.1 Study Endpoints

- Per patient and per region ⁶⁸Ga-PSMA-11 positivity.
- Biopsy correlation.

8.1.1 Randomization

There will be no randomization performed. There will be no blinding performed.

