8.2 Determination of Sample Size and Accrual Rate

8.2.1 Sample Size and Power Estimate

The primary endpoint is to evaluate the positive predictive value (PPV) on a (1) per-patient and (2) per-region-basis (prostate bed, pelvis, extrapelvic soft tissue, and bone metastases) of ⁶⁸Ga-PSMA-11 PET for detection of tumor location confirmed by histopathology/biopsy. Based on the results of previous studies, the following distribution of disease across the four regions are anticipated (19-21):

- a) Prostate bed: 30%
- b) Pelvis: 15%
- c) Extrapelvic soft tissue: 20%
- d) Bone metastases: 35%

It is anticipated that the PPV for the four regions and for all regions combined using conventional imaging ranges from 30-60%. An overall PPV for ⁶⁸Ga-PSMA-11 PET of at most 50% will be considered as unacceptably low. Hence, the null hypothesis that the PPV is at most 50% will be tested against the alternative hypothesis that the PPV is greater than 50%. It is hypothesized that ⁶⁸Ga-PSMA-11 PET imaging on the per-region and per-patient basis will substantially increase the PPV for the four regions to at least 70%. A sample size of 75 true positives is required for rejecting the null hypothesis that the PPV is at most 50% with 90% power at the one-sided 0.01 (=0.05/5 – a Bonferroni adjustment for evaluating the PPV for the four regions and for all regions combined) significance level, assuming an average regions specific prevalence of 20%. It is expected that approximately 25% of the accrued patients will undergo a biopsy. Hence, the proposed total number of patients requiring a biopsy is 375 in

order to power the analysis at a per region level. Assuming a prevalence rate of 20% for disease in each individual region, a total sample size of 1,500 patients is required. The following table shows the attainable power levels for detecting an increase in the PPV from 50% to 70% at the one-sided 0.01 significance level for the four disease regions and for all regions combined with the proposed sample size of 1500 patients:

Table: *Attainable power levels for detecting an increase in PPV from 50% to 70% with sample size of 1,500 patients (375 biopsies)*

	Prevalence	Number of Biopsies with True Positives	Power
Prostate bed	30%	113	98%
Pelvis	15%	56	78%
Extrapelvic soft tissue	20%	75	90%
Bone metastases	35%	131	>99%
All regions combined	100%	375	>99%

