8.3 Analyses Plans

8.3.1 Analysis Population

Patients with histopathology correlates will be analyzed for the Primary Aim. All remaining patients will be analyzed for the secondary endpoints.

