8.3.2 Analysis of Primary Endpoints

PPVs on a per-patient and per-region-basis of ⁶⁸Ga-PSMA-11 PET for detection of tumor location confirmed by histopathology/biopsy will be calculated and reported along with the corresponding two-sided 95% confidence intervals. The confidence intervals will be constructed using the Wilson score method.

a) Imaging interpretation ⁶⁸Ga-PSMA-11 PET:

PET images will initially be interpreted by a board certified nuclear medicine physician or a board certified radiologist experienced in reading PET at the time of the imaging study at the institution that the study is being performed. These interpretations will not be used for final evaluation. For the data sets included in the analysis for the Primary Endpoint, imaging data will be anonymized and collected at a central site. PET data will be interpreted by three different readers in a random order at separate reading sessions. ⁶⁸Ga-PSMA PET/CT reading training set and guides will be provided and completion of this training will be required for all central review readers.

Visual interpretation:

Regions of suspected disease will be graded on a two-point scale by each reader (0=Negative or 1= Positive). A region will be judged as positive if at least one lesion in this region is visually positive.

- i) Lymph nodes will be considered positive if the ^{68}Ga -PSMA-11 uptake is focal and greater than blood pool (adjacent or mediastinal blood pool). Pelvic lymph nodes will be subclassified according to their localization as follows: R/L obturator, R/L external iliac, R/L internal iliac and other (total of 7 subgroups).
 - ii) Visceral lesions will be considered positive if the ^{68}Ga -PSMA-11 uptake is focal and greater than physiologic background activity of the involvement organ or anatomic site.
 - iii) Bone lesions will be considered positive if the ^{68}Ga -PSMA-11 uptake is focal and greater than physiologic bone marrow.
 - iv) Prostate bed and prostate lesions will be considered positive if the ^{68}Ga -PSMA-11 uptake is focal and greater than physiologic background activity of the involvement organ or anatomic site.
- b) Follow-up Imaging:

All patients will be followed up 3-12 months with conventional imaging (dedicated CT, MRI and/or bone scan). Interpretation of follow-up imaging will be performed by local read. The follow-up conventional imaging should be the same modality/modalities as the initial staging work-up to allow for reproducible and accurate comparisons.

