- iii) ⁶⁸Ga-PSMA-11 positive bone lesions will be considered:
- (1) True positive:
- If there was a corresponding positive sclerotic lesion on the CT portion of the ⁶⁸Ga-PSMA-11 PET.
 - If there is focal uptake seen on the baseline bone scan performed within one month of ⁶⁸Ga-PSMA-11 PET.
 - If there is a lesion noted on the initial MRI performed within one month of ⁶⁸Ga-PSMA-11 PET.
 - If within 12 months follow-up CT demonstrates development of sclerosis.
 - If within 12 months follow-up MRI demonstrates a new bone lesion.
 - If within 12 months follow-up bone scan demonstrates new focal uptake.
- (2) False positive:
- If ⁶⁸Ga-PSMA-11 positive bone lesions do not meet the criteria for true positive findings.
- iv) ⁶⁸Ga-PSMA-11 positive prostate bed and prostate lesions will be considered:

(1) True positive:

- If on follow-up imaging within 12 months, lesions seen on CT or MRI decrease by 30% (for patients undergoing systemic treatment of focal therapy at this site) or increase by 20% in largest diameter..
- If patients with prostate bed lesions show a decrease of PSA by greater than 50% after targeted treatment (i.e. external beam radiation) and lesions do not change in size (less than 30% decrease or 20% increase in largest diameter).

(2) False positive:

- If on follow-up imaging within 3-12 months, sites of initial⁶⁸Ga-PSMA-11 positive lymph node lesions seen on CT or MRI decrease by more than 30% *without* systemic therapy or focal therapy at this site.
- If ⁶⁸Ga-PSMA-11 positive lymph node lesions do not meet the criteria for above false positive or true positive findings.

c) Histopathology/Biopsy:

- i) Localization of lesions for histopathology/biopsy will be classified according to the regions in table 1.
- ii) ⁶⁸Ga-PSMA-11 positive findings are aimed to be confirmed by histopathology/biopsy if clinically feasible.
- iii) Histopathological procedures and biopsies will be performed as clinically indicated and as per institutional protocol.

(1) Positive HP/Biopsy: Confirmed sites of metastatic or tumor involvement by histopathology/biopsy will be discussed with the responsible physician/surgeon.

(2) Negative Biopsy: Patients with suspected tumor recurrence on ⁶⁸Ga-PSMA-11 PET with negative histopathology/biopsy will be handled as outlined below:

(a) Lymph nodes:

- For patients undergoing nodal dissection: Patients will be rescanned with dedicated CT or MRI to determine if the suspicious ⁶⁸Ga-PSMA-11 positive node was removed.

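### The plan's only statement on blinding is that there is none, and nothing masks the central PET readers to histology, so the primary PPV is open to upward bias

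*Combined protocol and SAP*

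**What the plan says.** Section 8.1.1, headed Randomization, says that there is no randomization and then: "There will be no blinding performed". No qualification follows.

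Section 8.3.1 defines the primary analysis set: "Patients with histopathology correlates will be analyzed for the Primary Aim". Section 8.3.2 describes how their scans are read. A local physician reads each scan when it is done, but of these local reads the plan says "These interpretations will not be used for final evaluation". The reads that count are central: "For the data sets included in the analysis for the Primary Endpoint, imaging data will be anonymized and collected at a central site", and "PET data will be interpreted by three different readers in a random order at separate reading sessions". Central readers must complete a training set. Each reader grades each region negative or positive by eye, mainly on whether uptake is focal and exceeds a named background (blood pool, marrow, or the organ or site involved).

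On biopsy, section 8.3.2(c) says that PET-"positive findings are aimed to be confirmed by histopathology/biopsy if clinically feasible".

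Section 8.2.1 sets the hypothesis: a PPV of at most 50% is to be rejected in favor of a higher value, at one-sided 0.01.

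**The concern.** PPV counts only positive calls. A reader who knows that a biopsied region was histologically negative can grade a borderline focus as negative. That region then leaves the denominator as well as the false-positive count, and PPV rises. The reported PPV would not show that this had happened.

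The plan sets aside the read made at the time of imaging, which comes before any biopsy that the scan could have prompted. It relies on a later-defined set of scans that qualify through the existence of histology. A site or reading center could follow the text exactly and still let the readers see the pathology. The 50% null could then be rejected partly because of how the scans were read. Reanalysis cannot remove such a bias; only a fresh masked read could.

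**Working it through.** **The text.** Sections 8.1.1, 8.3.1 and 8.3.2 were read together. The safeguards named are anonymization, central collection, three trained readers, random order and separate sessions. Anonymization removes identity. Random order and separate sessions limit carry-over between reads. Training and the uptake criteria limit discretion. None of them says that histology, follow-up imaging or the local report is withheld. The time of the central reads relative to biopsy is not given.

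**The plan's own figure.** Inputs from section 8.2.1: null PPV 0.50, alternative 0.70, one-sided alpha 0.01, power 90%, stated n = 75.

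n = [z(0.99)·√(0.5·0.5) + z(0.90)·√(0.7·0.3)]² / 0.2² = 76.6, so 77. This is within 2 of the stated 75. The same approximation gives power of 89.3% at n=75 (stated 90%) and above 99.9% at n=375 (stated >99%). The figures therefore behave as denominators of PPV, and are used that way here. Masking changes none of these inputs.

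**Size of a possible bias.** Assumption, not in the documents: readers change a share q of histology-negative positive calls to negative, and leave histology-positive calls alone. True PPV is 0.50.

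Apparent PPV = 0.5 / [0.5 + 0.5(1 − q)]

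- q = 0.10: 0.5/0.95 = 52.6%
- q = 0.20: 0.5/0.90 = 55.6%
- q = 0.30: 0.5/0.85 = 58.8%

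The plan names no test statistic, so an exact binomial test at 0.01 was used. The cutoff is 49 or more of 75 (exact level 0.0053) and 211 or more of 375 (0.0087). A cutoff of 48 of 75 has level 0.0101, just over 0.01, and was not used.

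Three ways of treating the denominator:

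- A: n stays at 75 or 375, with the apparent PPV as success probability.
- B: n shrinks to its expected size n(1 − q/2), rounded, with its own cutoff. From 75 this gives 71, 68 and 64 calls (cutoffs 46, 45, 42). From 375 it gives 356, 338 and 319 (cutoffs 201, 191, 181).
- C: the number of calls left is random, binomial with n and probability 1 − q/2. The rejection probability is averaged over it, with the exact cutoff for each size.

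| q | n=75: A | B | C | n=375: A | B | C |
|---|---|---|---|---|---|---|
| 0 | 0.5% | 0.5% | 0.5% | 0.9% | 0.9% | 0.9% |
| 0.10 | 1.8% | 2.6% | 2.3% | 8.7% | 8.2% | 8.3% |
| 0.20 | 5.5% | 4.9% | 6.1% | 41.2% | 38.4% | 36.9% |
| 0.30 | 15.2% | 16.4% | 14.7% | 85.5% | 79.2% | 78.3% |

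At q = 0.05 the apparent PPV is 51.3%, and false rejection is 1.0% to 1.6% at n=75 and 2.9% to 3.1% at n=375. The inflation grows with n because a fixed bias is tested with more precision.

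**The case against.** The strongest reply is that the sentence in section 8.1.1 is template text. It follows a statement that there is no randomization, in a study described as open label, and it most naturally refers to treatment. This stands. A reader might infer that the plan orders unmasked reading, and the documents do not support that. Reader masking is left unspecified, not refused. The gap remains on this reading, because masking is then stated nowhere.

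Second, the reading process has real safeguards, and what is sent to the central site is described as imaging data. No section sends pathology, PSA or local reports to the readers. This also stands: the documents do not show that readers will learn the result. They also do not rule it out. Section 8.3.2(c), for instance, has procedure images reviewed after a negative needle biopsy without saying who does so.

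Third, a reader might infer that scans are collected and read only after histology is known. Sections 8.3.1 and 8.3.2 suggest this, since a scan joins the primary set only through histology, but the timing of transfer and reading is not stated. Knowing that histology exists also does not reveal whether it was positive.

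Fourth, the size rests wholly on an assumed rate of changed calls. That is correct. The direction follows from how PPV is built; the amount cannot be taken from the documents.

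**Conclusion.** The text is wrong as written. It states that there is no blinding, without exception, while the primary PPV depends on visual calls by readers whom no section masks to the reference standard. The conclusion is that the plan permits an upward bias, not that the bias will occur or that the reads are known to be unmasked.

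The size is conditional on a true PPV of 50%, calls changed only in histology-negative regions, and the assumed rate of change. Over rates of 10% to 30%, the nominal 1% error becomes about 2% to 16% at the per-region design number of 75, and about 8% to 86% at 375 for all regions combined. At a rate of 5% the per-region effect is slight. Confidence in the direction is high; the amount is illustrative.

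**What to change.** In section 8.1.1, replace the sentence on blinding with: 'Treatment is open label.'

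In section 8.3.2, under imaging interpretation, add: 'The three central readers will be masked to histopathology and biopsy results, follow-up imaging and the local PET interpretation. Their reads will be locked before they are linked to the reference standard.'

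Masking to PSA and to baseline conventional imaging is optional, since the problem here is knowledge of the reference standard. Mixing in scans from patients without biopsy is a further option: masked readers would otherwise still know that every scan in the set has histology, and that PET-positive findings are the ones aimed at for biopsy.

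The cost of the two edits is wording only. The central readers and the anonymized transfer are already planned, and no sample-size input changes. The optional extra scans would add reading time.

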8.2 Determination of Sample Size and Accrual Rate

8.2.1 Sample Size and Power Estimate

The primary endpoint is to evaluate the positive predictive value (PPV) on a (1) per-patient and (2) per-region-basis (prostate bed, pelvis, extrapelvic soft tissue, and bone metastases) of ⁶⁸Ga-PSMA-11 PET for detection of tumor location confirmed by histopathology/biopsy. Based on the results of previous studies, the following distribution of disease across the four regions are anticipated (19-21):

- a) Prostate bed: 30%
- b) Pelvis: 15%
- c) Extrapelvic soft tissue: 20%
- d) Bone metastases: 35%

It is anticipated that the PPV for the four regions and for all regions combined using conventional imaging ranges from 30-60%. An overall PPV for ⁶⁸Ga-PSMA-11 PET of at most 50% will be considered as unacceptably low. Hence, the null hypothesis that the PPV is at most 50% will be tested against the alternative hypothesis that the PPV is greater than 50%. It is hypothesized that ⁶⁸Ga-PSMA-11 PET imaging on the per-region and per-patient basis will substantially increase the PPV for the four regions to at least 70%. A sample size of 75 true positives is required for rejecting the null hypothesis that the PPV is at most 50% with 90% power at the one-sided 0.01 (=0.05/5 – a Bonferroni adjustment for evaluating the PPV for the four regions and for all regions combined) significance level, assuming an average regions specific prevalence of 20%. It is expected that approximately 25% of the accrued patients will undergo a biopsy. Hence, the proposed total number of patients requiring a biopsy is 375 in

order to power the analysis at a per region level. Assuming a prevalence rate of 20% for disease in each individual region, a total sample size of 1,500 patients is required. The following table shows the attainable power levels for detecting an increase in the PPV from 50% to 70% at the one-sided 0.01 significance level for the four disease regions and for all regions combined with the proposed sample size of 1500 patients:

Table: *Attainable power levels for detecting an increase in PPV from 50% to 70% with sample size of 1,500 patients (375 biopsies)*

	Prevalence	Number of Biopsies with True Positives	Power
Prostate bed	30%	113	98%
Pelvis	15%	56	78%
Extrapelvic soft tissue	20%	75	90%
Bone metastases	35%	131	>99%
All regions combined	100%	375	>99%

In summary, the proposed target accrual of 1,500 patients (375 with biopsies) will provide adequate power for detecting the anticipated improvement in the PPV for both the per-patient and per-region based ⁶⁸Ga-PSMA-11 PET imaging when compared to conventional imaging. However, a sample size of 107 patients with biopsies in total is sufficient for detecting the anticipated improvement in PPV when evaluating per-patient based positive predictive value.

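### Single-step Bonferroni over the five primary PPV tests is valid but needlessly weak: if PPV is 70% in every region, Holm's step-down raises pelvis power from about 78% to 91% with no added patients

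*Combined protocol and SAP*

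**What the plan says.** Section 8.2.1 sets out the test: "the null hypothesis that the PPV is at most 50% will be tested against the alternative hypothesis that the PPV is greater than 50" percent. The design alternative is that PSMA PET "will substantially increase the PPV for the four regions to at least 70" percent. There are five such hypotheses, one for each of four regions and one for all regions combined. The sizing is done "with 90% power at the one-sided 0.01 (=0.05/5", and the divisor of 5 is explained as "a Bonferroni adjustment for evaluating the PPV for the four regions and for all regions combined".

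The power table ("Attainable power levels for detecting an increase in PPV from 50% to 70% with sample size of 1,500 patients") applies 0.01 to every row. Its counts and powers are: prostate bed 113, 98%; pelvis 56, 78%; extrapelvic soft tissue 75, 90%; bone 131, >99%; combined 375, >99%. Pelvis is the only row below 90%. The closing summary of 8.2.1 says that the accrual "will provide adequate power for detecting the anticipated improvement in the PPV for both the per-patient and per-region based" analyses.

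No step-down procedure appears anywhere. Section 8.3.2 describes the primary analysis only as PPVs with two-sided 95% Wilson intervals. It names no test, no alpha and no multiplicity rule.

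**The concern.** Under single-step Bonferroni each hypothesis faces 0.01 whatever the other four show. By the plan's own table, three of the five tests (combined, bone, bed) have 98% power or more, so on the design assumptions they are nearly always rejected. Once they are, single-step Bonferroni makes no further use of their share of alpha, while pelvis and extrapelvic soft tissue are still tested at 0.01.

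Per-region PPV is part of the primary objective (section 2.1), and the figure of 375 biopsies was chosen to power the regional analyses. At stake is power in the smaller regions that the same data could supply under the same nominal error bound.

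**Working it through.** **Inputs (8.2.1).** Null PPV 0.50; alternative 0.70 in every region; familywise alpha 0.05 one-sided; five tests; counts 113, 56, 75 and 131, which sum to 375. Two assumptions are needed: the counts are PPV denominators, and each biopsied patient contributes one region, so that the regions are independent and the combined count is their sum.

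**Reproducing the plan.** Normal-approximation power is Φ((√n × 0.2 − z × 0.5)/√0.21), with z = 2.326 at 0.01. For pelvis: (7.483 × 0.2 − 1.163)/0.458 = 0.728, so 76.7%. The other rows give 98.2% (bed), 89.3% (extrapelvic), 99.3% (bone) and over 99.9% (combined). All are close to the printed figures.

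On binomial data the pelvis score test at 0.01 needs at least 28 + 2.326 × 3.742 = 36.7, so 37 of 56. That has power 78.7%, close to the printed 78%, but its true level is 1.11%. The exact test needs 38 of 56, with power 69.5%.

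**Why Holm cannot lose.** Holm compares the ordered p-values with 0.05/5, 0.05/4, 0.05/3, 0.05/2 and 0.05, stopping at the first failure. Any p-value at or below 0.01, and every smaller one, passes its own threshold, so every Bonferroni rejection is kept. With m true nulls, the first one rejected must have p ≤ 0.05/m. The union bound then gives at most 5% under any dependence. This is needed here because the combined test shares data with the regional tests.

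**Where the gain comes from.** When the other four are rejected, pelvis is tested at 0.05. The cut-off is then 28 + 1.645 × 3.742 = 34.2, so 35 of 56. The exact test has the same cut-off, with level 4.07% and power 91.3%.

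**Simulation (400,000 trials, PPV 70% everywhere), Bonferroni to Holm:**

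| Test | Score | Exact |
|---|---|---|
| Prostate bed | 98.4% to 99.6% | 97.4% to 99.5% |
| Pelvis | 78.5% to 91.0% | 69.6% to 90.9% |
| Extrapelvic | 89.5% to 97.3% | 84.4% to 95.5% |
| Bone | 99.3% to 99.9% | 98.9% to 99.8% |
| All five succeed | 68.6% to 88.5% | 56.5% to 86.9% |

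**Pelvis power when other regions are truly at 50%, Bonferroni to Holm:**

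| Regions at 50% | Score | Exact |
|---|---|---|
| Extrapelvic | 78.6% to 86.0% | 69.3% to 85.7% |
| Bed and extrapelvic | 78.6% to 85.3% | 69.5% to 78.7% |
| Bed, extrapelvic and bone | 78.7% to 78.8% | 69.5% to 70.1% |

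**Realised familywise error.** With score tests and bed and extrapelvic at 50%, it rises from about 2.2% under Bonferroni to 5.7–5.8% (across simulation runs) under Holm. The score test's own approximation carries it past 5%. With exact tests, Holm's realised error was at most about 4% in every configuration tried.

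**Cost of the same gain by recruitment.** Pelvis power of 90% under Bonferroni needs ((2.326 × 0.5 + 1.282 × 0.458)/0.2)² = 76.6, so 77 pelvic biopsies. At the plan's 15% and 25% rates that is 77/(0.15 × 0.25) ≈ 2,050 patients, about 550 more than planned.

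**The case against.** The strongest reply is that nothing here is wrong. Bonferroni controls the error rate that the plan sets, and the 78% for pelvis is printed openly. That stands. A reader might infer that the plan misses its own 90% target for pelvis, but the documents do not support this. The 90% belongs to the sizing step ("A sample size of 75 true positives is required"), which assumes an average regional prevalence of 20%. The table then reports what each region attains, and 90% is nowhere promised for pelvis.

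A reader might also infer that 1,500 patients would give at least 90% power in every region under Holm. That is true only if PPV is 70% in all of them. This is the plan's design hypothesis, but it is not a known fact, and the second table shows how the gain shrinks without it.

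Thirdly, the same familywise error means the same upper bound. Realised error is higher than under Bonferroni, and the bound needs valid p-values. This also stands, and it is the reason to require exact tests.

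Finally, the table's column heading describes the counts as true-positive biopsies, and the 107 in the summary equals 75/0.70, which fits 75 as a numerator. If 56 were true positives, 56/0.70 = 80 biopsied PET-positive findings would already give about 91% for pelvis under Bonferroni. The printed powers, however, fit the counts as denominators: 76.7% at n = 56 and 91.4% at n = 80, against the printed 78%. The label needs clearing up separately. It affects the size of the gain, but not the fact that Holm rejects at least as much as Bonferroni.

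**Conclusion.** The multiplicity method is valid but weaker than it needs to be. With PPV 70% in every region, the tabulated counts as denominators and independent regions, Holm adds about 12 points of pelvis power with score tests and about 21 with exact tests. It adds 20 and 30 points respectively to the chance that all five succeed. With one other region at 50%, pelvis power is about 86%. With bed and extrapelvic at 50% it is 79% (exact) to 85% (score). With all three others at 50% it is essentially unchanged. In no case is it lower than under Bonferroni with the same test. This is a free improvement and does not call the planned error control into question.

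**What to change.** - **8.2.1:** replace the Bonferroni level of 0.01 per test with Holm's step-down over the five p-values at familywise one-sided 0.05. Add a Holm column to the power table and state beside it that the figures assume PPV 70% in all regions.
- **8.3.2:** add that the five p-values come from exact one-sided binomial tests of PPV at most 50% and are judged by Holm. This is new text, since the section names no test now.
- Keep the 95% Wilson intervals and label them descriptive.
- Make the change before the primary data are analysed.

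The cost is a sentence in each section and one table column, with no added patients and no change to trial conduct. The one drawback is that Holm has no simple matching simultaneous intervals. The plan does not provide such intervals now, so nothing is given up.

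### Section 8.2.1 claims power for an improvement over conventional imaging, but the calculation is a one-sample test against a fixed PPV of 50%

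*Combined protocol and SAP*

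**What the plan says.** Section 8.2.1 of the combined protocol and SAP gives a range for the comparator: "It is anticipated that the PPV for the four regions and for all regions combined using conventional imaging ranges from 30-60"%. It then sets 50% as the PPV at or below which PSMA PET would not be acceptable, and states the test: "the null hypothesis that the PPV is at most 50% will be tested against the alternative hypothesis that the PPV is greater than 50"%. The alternative is that PSMA PET "will substantially increase the PPV for the four regions to at least 70"%. The size is fixed by "A sample size of 75 true positives is required for rejecting the null hypothesis" "with 90% power at the one-sided 0.01 (=0.05/5", a Bonferroni split over four regions plus all regions combined), at an average regional prevalence of 20%.

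The power table is captioned as an increase from 50% to 70%. It gives prostate bed (113) 98%, pelvis (56) 78%, extrapelvic soft tissue (75) 90%, bone (131) above 99% and all regions (375) above 99%.

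The closing summary says that the target accrual "will provide adequate power for detecting the anticipated improvement in the PPV", per patient and per region, for PSMA "PET imaging when compared to conventional imaging". It adds that 107 biopsied patients would suffice for the per-patient PPV.

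Section 8.3.2 analyses the primary endpoint as PPVs with 95% Wilson intervals and has no comparator. Section 8.3.3 compares PPVs with conventional imaging by a paired McNemar test, as a secondary analysis.

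**The concern.** The summary gives the design a comparative property that was never calculated. A comparison with conventional imaging would need conventional-imaging results, their variance and the pairing between the two modalities. None of these appears in section 8.2.1.

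The 50% benchmark cannot stand in for conventional imaging, because it lies inside the 30-60% that the plan itself expects for conventional imaging. If a region's conventional PPV is above 50%, PSMA PET could reject the null there without being better.

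Section 1.1 says that the data are to be pooled for an NDA submission. A reader who relies on the summary could take a rejected null as adequately powered evidence of improvement over conventional imaging. The primary test supports only a PPV above 50%.

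**Working it through.** **Inputs (all from section 8.2.1).** p1 = 0.70; p0 = 0.50; one-sided alpha = 0.05/5 = 0.01, so z = 2.326; n = 56, 75, 113, 131 and 375 from the table; 107 from the summary; conventional PPV 0.30-0.60.

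**Assumption on n.** The table heads its counts as biopsies with true positives. I take them as PPV denominators (biopsied PET-positive findings), because that reading reproduces the table.

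**Step 1: reproduce the table.** One-sample normal approximation:

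power = Φ{[√n(p1 − p0) − z√(p0(1 − p0))] / √(p1(1 − p1))}

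For n = 56: √56 × 0.20 = 1.497; 2.326 × 0.5 = 1.163; √0.21 = 0.458; (1.497 − 1.163)/0.458 = 0.73; Φ = 0.767.

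| | n | Plan | Recomputed, 50% vs 70% |
|---|---|---|---|
| Pelvis | 56 | 78% | 76.7% |
| Extrapelvic soft tissue | 75 | 90% | 89.3% |
| Prostate bed | 113 | 98% | 98.2% |
| Bone | 131 | >99% | 99.3% |
| All regions | 375 | >99% | >99.9% |

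The same formula solved for 90% power gives n = [(2.326 × 0.5 + 1.282 × 0.458)/0.20]² = 76.6, so 77 against the stated 75. The table is therefore a one-sample calculation against a fixed 50%.

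**Step 2: move the fixed benchmark across the plan's range.** Exact binomial: take the smallest c with P(X ≥ c | n, p0) ≤ 0.01; power is P(X ≥ c | n, 0.70). For n = 56 and p0 = 0.60, c = 43 and power is 16.8%.

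| n | p0 = 40% | 45% | 50% | 55% | 60% |
|---|---|---|---|---|---|
| 56 | 98.6% | 91.3% | 69.5% | 47.3% | 16.8% |
| 75 | 99.8% | 97.6% | 84.3% | 60.6% | 22.7% |
| 113 | >99.9% | 99.9% | 97.4% | 82.8% | 39.2% |
| 131 | >99.9% | >99.9% | 98.9% | 88.1% | 52.0% |
| 375 | >99.9% | >99.9% | >99.9% | >99.9% | 95.3% |

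At 30% every entry exceeds 99.9%. At p0 = 60% the normal approximation gives 19.7%, 27.5%, 43.4%, 50.4% and 95.9%, in the same order of n.

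**Step 3: the 107 biopsies.** Against 50%, power is 97.4% exact and 97.6% by normal approximation, so 107 is ample for that benchmark. Against 60% it is 37.3% exact and 40.9% by normal approximation.

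**What step 2 does not measure.** It still treats the conventional PPV as known without error, so it is not the power of a comparison. The power of the paired test in section 8.3.3 depends on discordance between the modalities, which the documents do not give.

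**The case against.** The strongest reply is that nothing is hidden. The null, the alternative, alpha and each region's power are printed just before the summary, and the table caption says 50% to 70%. On this view the summary's comparison is shorthand for the benchmark, and no analysis or decision rule depends on it. The disclosure is real, and it is why the design itself is not at fault. The shorthand reading does not hold, though. Section 8.2.1 sets 50% as an acceptability floor, separately from the 30-60% it expects of conventional imaging, and the floor lies inside that range.

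Three stronger readings are tempting and should not be drawn.

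- *Regional power is really 17-52%.* That is one corner: conventional PPV at the top of its range in all four regions, and PSMA PPV at the bottom of what the plan hypothesises. At a conventional PPV of 45%, the middle of the range, exact power is 91% or more in every region. If the PSMA PPV were 80% (an assumption; the plan says at least 70%), exact power against 60% would be 78%, 90%, 99% and above 99% for n = 56, 75, 113 and 131.
- *Per-patient power fails.* With all 375 biopsies it is about 95% even against 60%. Only the 107 figure falls short.
- *The pelvis misses a 90% target.* The plan attaches 90% to 75 findings at 20% prevalence and does not set it for every region. The pelvic 78% is printed openly, and whether it is adequate is a judgement.

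The label on the counts also matters. If they were true positives, the regional denominators at a PPV of 70% would be n/0.70, about 80, 107, 161 and 187, and exact power against 60% would be 27-65%. The conclusion would be the same.

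**Conclusion.** The point holds as a misstatement of what the sample size delivers. The tabulated power is for excluding a fixed PPV of 50%. The documents contain no power calculation for a comparison with conventional imaging, and excluding 50% does not establish an improvement where the conventional PPV exceeds 50%. This conclusion rests on the text and on reproducing the table to within 2 points.

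The size of the gap is illustrative. It assumes a PSMA PPV of 70%, one-sided 0.01, the table counts as denominators, and a known conventional PPV. On those terms regional power is satisfactory if the conventional PPV is 45% or below, falls below 90% in every region at 55%, and is 17-52% at 60%. The documents do not support calling the trial underpowered, or rejecting the 50% null as a design.

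**What to change.** Reword the closing paragraph of section 8.2.1 to say three things:

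- The sample size gives the tabulated power to exclude a fixed PPV of 50%, including 78% in the pelvis.
- The 107-biopsy figure refers to the same 50% benchmark.
- No power is claimed for the comparison with conventional imaging in section 8.3.3.

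A sensitivity display beside the table is optional. If one is added, it should span the plan's whole 30-60% range, not 60% alone, and be labelled as power against a fixed benchmark and not as comparative power.

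The cost is a less favourable stated claim. Enrolment, the primary test and the planned analyses do not change.
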